## ABBREVIATIONS

Activation Function – AF  
Adverse event – AE  
Alanine transaminase – ALT  
American Society of Anesthesiologists – ASA  
ANC – Absolute neutrophil count  
Androgen deprivation therapy – ADT  
Androgen Receptor – AR  
Androgen Response Element – ARE  
Area under the concentration-time curve – AUC  
Aspartate transaminase – AST  
Blood Urea Nitrogen – BUN  
Cancer Therapy Evaluation Program – CTEP  
Case Report Form – CRF  
Castration resistant prostate cancer – CRPC  
Circulating Tumor Cells – CTCs  
Code of Federal Regulations – CFR  
Complete response – CR  
Partial response – PR  
Computed tomography – CT  
Confidence interval – CI  
Ligand binding domain – LBD  
Dana-Farber Cancer Institute – DFCI  
Dana-Farber/Harvard Cancer Center – DF/HCC  
Dana-Farber/Partners Cancer Care – DF/PCC  
Data Safety and Monitoring Committee – DSMC  
Dehydroepiandrosterone – DHEA  
Dehydroepiandrosterone-sulfate – DHEA-S  
Deoxyribonucleic acid – DNA  
Diastolic blood pressure – DBP  
Dihydrotestosterone – DHT  
DNA binding domain – DBD  
Eastern Cooperative Oncology Group – ECOG  
Echocardiogram – ECHO  
Electrocardiogram – EKG  
Fluoro-dihydrotestosterone-positron emission tomography – FHDT-PET  
Food and Drug Administration – FDA  
Good Clinical Practice – GCP  
Half-life –  $t_{1/2}$   
Hazard ratio – HR  
Health Insurance Portability and Accountability Act – HIPAA  
Heat Shock Protein – HSP  
Hematoxylin and eosin – H&E  
Human immunodeficiency virus – HIV  
Immunohistochemistry – IHC

CONFIDENTIAL

[figure not shown]
This document is confidential. Do not disclose or use except as authorized.

Institutional Review Board – IRB  
International Normalized Ratio – INR  
Investigational New Drug – IND  
Laser capture microdissection – LCM  
Liver function test – LFT  
Luteinizing hormone-releasing hormone – LHRH  
Magnetic Resonance Imaging – MRI  
Maximum plasma concentration –  $C_{\max}$   
Messenger RNA – mRNA  
Systolic blood pressure – SBP  
Minimum plasma concentration –  $C_{\min}$   
Multi Gated Acquisition Scan – MUGA  
National Cancer Institute Common Terminology Criteria for Adverse Events – NCI CTCAE  
New York Heart Association – NYHA  
Not Reached – NR  
N-Terminal Domain – NTD  
Office of Data Quality- ODQ  
Office for Human Research Studies – OHRS  
Overall survival – OS  
Partial thromboplastin time – PTT  
Positron emission tomography – PET  
Principal Investigator – PI  
Progression free survival – PFS  
Progressive disease – PD  
Prostate specific antigen – PSA  
Prostate Cancer Working Group – PCWG  
Prothrombin time – PT  
Response Evaluation Criteria In Solid Tumors – RECIST  
Reverse transcription polymerase chain reaction – RT-PCR  
Ribonucleic acid – RNA  
Serious adverse event – SAE  
Single-nucleotide polymorphism – SNP  
Skeletal Related Event – SRE  
Single-photon emission computed tomography - SPECT  
Stable disease – SD  
Time to PSA Progression – TTPP  
Unknown – UN  
Upper limit of normal – ULN  
WBC – White blood cell count

CONFIDENTIAL

This document is confidential. Do not disclose or use except as authorized.

## SCHEMA

1. Population: Metastatic CRPC patients.
2. Treatment: Participants will be treated with enzalutamide in 28-day cycles. Participants will be continued on the study until symptomatic or radiographic progression.
3. Planned Enrollment: 66 participants across multiple sites.
4. Study Duration:
  - a. Enrollment – one year.
  - b. Sample collection and analysis – two years.
  - c. Final report – 3-6 months after the end of data collection.
5. Data Safety Monitoring Committee (DSMP)/Safety Review: Quarterly.

CONFIDENTIAL

This document is confidential. Do not disclose or use except as authorized.

## 1. OBJECTIVES

The primary objective of this trial is to analyze possible AR related mechanisms of resistance to enzalutamide. Samples of CRPC will be obtained at baseline and at progression on treatment with enzalutamide. Tumor analysis will include AR sequencing (mutations, splice-variants), AR regulated gene expression, tumor androgen levels, profiling of enzymes involved in androgen synthesis/metabolism, and whole-exome and transcriptome sequencing. Secondary objectives include assessment of clinical response and correlation of clinical response to alterations in the AR signaling axis. Exploratory analyses will be to analyze circulating tumor cells (CTCs) for AR nuclear localization, AR splice variant expression and AR sequence. Additionally, we will analyze circulating tumor DNA.

### 1.1 Study Design

This is a phase II, prospective, multicenter, single-arm study accessing mechanisms of resistance to enzalutamide in participants with metastatic CRPC.

### 1.2 Primary Objectives

- To analyze possible AR related mechanisms of resistance to enzalutamide in serial CRPC biopsies including AR sequencing (mutations, splice variants), AR regulated gene expression, tumor androgen levels, profiling of enzymes involved in androgen synthesis/metabolism, and whole-exome and transcriptome sequencing.

### 1.3 Secondary Objectives

- Assess changes in serum androgen concentrations (including testosterone, dihydrotestosterone (DHT), and androgen precursors) between baseline and subsequent assessment visits.
- To assess prostate specific antigen (PSA) response to enzalutamide.
- To assess PSA response duration to enzalutamide.
- To assess response of measurable disease to enzalutamide.
- To assess duration of response of measurable disease to enzalutamide.
- To assess safety and tolerability of enzalutamide.
- To correlate alterations in AR mutation, AR splice variants, TMPRSS2/ERG, AR regulated gene expression, tumor androgens, serum androgens, whole-exome and transcriptome sequencing with PSA and radiographic response to enzalutamide.

CONFIDENTIAL

This document is confidential. Do not disclose or use except as authorized.

- To investigate subsequent lines of therapy, including line of agent, name of agent, and PSA kinetics following study drug discontinuation and correlate with response to study drug.

#### **1.4 Exploratory Objectives**

- To measure circulating tumor cells (CTCs) as a marker of response to enzalutamide.
- To analyze CTCs for mechanisms of AR resistance including AR nuclear localization, AR splice variant expression and AR sequence.
- To analyze circulating tumor DNA for mechanisms of AR resistance and correlate to response to enzalutamide.
- To explore the association between quantitative  $^{99m}\text{Tc}$ -MDP uptake in skeletal metastases, measured as activity concentration on quantitative SPECT/CT, with anatomical bone findings on CT, laboratory tumor markers (e.g. PSA, circulating tumor DNA) and overall response in an imaging substudy of patients enrolled at the Dana-Farber Cancer Institute only.

CONFIDENTIAL

This document is confidential. Do not disclose or use except as authorized.

## 2. BACKGROUND

### 2.1 Study Agent(s)

#### 2.1.1 Enzalutamide

Enzalutamide, formerly known as MDV3100, is a rationally-designed second generation AR inhibitor which functions by blocking several steps in the AR signaling cascade. Enzalutamide competitively binds the AR with great potency. Additionally, enzalutamide inhibits nuclear translocation of activated AR and inhibits the association of activated AR with DNA.

#### **Rational for Using Enzalutamide in Prostate Cancer**

First generation antiandrogens, including bicalutamide, nilutamide, and flutamide, are reversible inhibitors of the AR and have a several-fold lower affinity to the AR compared with androgens. These agents have been used in the management of advanced prostate cancer for decades. Addition of an antiandrogen at the time of CRPC has been shown to lower PSA by 50% or more in approximately one-quarter of patients. There is no data supporting the superiority of one antiandrogen over another, however nilutamide has been shown to induce PSA declines in men who have developed resistance to AR inhibition with flutamide or bicalutamide.

It was first noted in the early 1990s that disease progression, despite the combination of an LHRH (luteinizing hormone-releasing hormone) agonist and an antiandrogen, could be stopped and reversed simply through discontinuation of the antiandrogen. Stopping the antiandrogen in men with a rising PSA, termed antiandrogen withdrawal, can result in PSA declines in between 10-20% of men. Further work demonstrated that in the setting of AR overexpression or mutation, conventional antiandrogens have the potential to exhibit paradoxical partial agonist activity, promoting prostate cancer progression. Thus, more potent antagonists lacking agonist activity are necessary.

#### **Preclinical Data with Enzalutamide**

Using the nonsteroidal agonist RU59603 as the parent scaffold compound, Sawyers and colleagues identified two oral diarylthiohydantoins, RD162 and enzalutamide, from a screen of nonsteroidal antiandrogens that retain antiandrogen activity in the setting of increased AR expression. Both compounds have enhanced affinity for the AR (5-8 fold) compared to the antiandrogen bicalutamide. Enzalutamide competitively binds the AR with an IC50 of 36 nM compared to 160 nM for bicalutamide. Additionally, enzalutamide inhibits nuclear translocation of activated AR, inhibits DNA binding to androgen response elements, and inhibits recruitment of coactivators, even in the setting of AR overexpression and in prostate cancer cells resistant to antiandrogens. By

CONFIDENTIAL

This document is confidential. Do not disclose or use except as authorized.

contrast with bicalutamide, enzalutamide is a pure antagonist with no detectable agonist effects in LNCaP/AR prostate cells, which overexpress AR. The drug also induces regression of established LNCaP/AR xenograft tumors growing in castrated male mice, a model in which bicalutamide treatment only slows tumor growth.

### **Clinical Data with Enzalutamide**

A phase I/II first in man study was initiated in July 2007 at three sites to assess safety, pharmacokinetics, tolerability, and antitumor activity. Patients with progressive, metastatic CRPC were eligible. The initial dose of enzalutamide was 30 mg daily, with subsequent dose-escalations in cohorts of 3-6 patients to a maximum dose of 600 mg daily. When significant >50% declines in PSA levels were observed in the first six patients, enrollment was expanded by an additional 24 patients (12 pre-chemotherapy, 12 post-chemotherapy) at every dose level starting at 60 mg daily. By 12/2008, 140 patients had been enrolled.

After administration of one dose, the drug was rapidly absorbed, and median time to  $C_{max}$  was one hour (range 0.42 minutes – 4 hours). The  $t_{1/2}$  was about 1 week (range 3 – 10 days) and was not affected by dose. Full pharmacokinetic profiles were linear and consistent over the dose range study. Plasma concentrations reached steady state after one month of treatment. Once achievement of steady state, the  $C_{min}$  in individual patients remained constant for several months, suggesting time-linear pharmacokinetics. Due to slow clearance from plasma, the daily fluctuation in steady-state enzalutamide concentrations were low. The mean  $C_{max}/C_{min}$  was 1.2 (range 1.14-1.3) indicating that the average difference between the peak and trough concentrations was  $\leq 30\%$ . AR binding was assessed in 22 patients at doses from 60-480 mg daily with FHDT-PET. All patients showed clear reduction of FDHT uptake (range 20-100%).

Fatigue was the most frequently reported AE, with dose-dependent increases of grade 3 fatigue (0% at 150 mg/day, 9% at 240 mg/day, 15% at 360 mg/day, and 20% at 480 mg/day). The dose of 240 mg/day was defined as the maximum tolerated dose. At doses of 240 mg and above, an increasing proportion of patients needed dose reductions for fatigue. Dose reductions were needed in 1 of 29 patients (3%) that received 240 mg/day, 3 of 28 patients (11%) that received 360 mg/day, and 5 of 22 patients (23%) that received 480 mg/day, and 0 of 58 patients that received 30, 60, or 150 mg/day. After dose reductions, the symptoms resolved. Only 1 patient discontinued treatment due to fatigue with an onset coinciding with PSA rise. Overall, the most common mild (grade 2) AEs were fatigue (n = 38, 27.1%), nausea (n = 12, 8.6%), dyspnea (n = 11, 7.9%), anorexia (n = 8, 5.7%), and back pain (n = 8, 5.7%). Fatigue, nausea, and anorexia were the only mild AEs with an increasing incidence as the dose of enzalutamide was increased. None of the grade 2 events required dose modification or the discontinuation of treatment, apart from 1 patient treated at 480 mg/day who had nausea at baseline and stopped therapy after 7 weeks.

CONFIDENTIAL

This document is confidential. Do not disclose or use except as authorized.

Two witnessed seizures occurred in patients receiving doses of 600 and 360 mg/day, and 1 possible seizure occurred at 480 mg/day. Whether enzalutamide was responsible for these seizures is unclear, since both patients who had witnessed seizures were concurrently taking drugs that could contribute to a lowered seizure threshold (olanzapine and prochlorperazine for the patient receiving 600 mg/day; methylphenidate for the patient receiving 360 mg/day). Both patients also had complicated medical problems that could have contributed to their seizures, including hypocalcaemia requiring intravenous calcium, anemia requiring red-cell transfusions, and skull metastases requiring skull radiation. Other causes of treatment discontinuation included rash in 1 patient that received 480 mg/day after 10 days and in 1 patient that received 600 mg/day after 3 days, and a myocardial infarction after 15 weeks of therapy in a patient with a history of diabetes, hypertension, and hypercholesterolemia that received 360 mg/day. All patients recovered without sequelae. No deaths and no other drug-related SAEs were reported.

In regards to efficacy, antitumor effects were noted at all doses including >50% declines in PSA in 78 (56%) patients, response in soft tissue in 13 (22%) of 59 patients, stabilized bone disease in 61 (56%) of 109 patients, and conversion from unfavorable to favorable CTC counts in 25 (49%) of 51 patients. Disease regression was dose dependent between daily doses of 30 mg and 150 mg, however no additional benefit was noted above this threshold.

Based on these results, two placebo-controlled, randomized phase 3 studies (AFFIRM and PREVAIL) were initiated to evaluate the efficacy and safety of enzalutamide in patient with advanced prostate cancer. The AFFIRM study evaluated the safety and efficacy of enzalutamide in 1,199 patients with CRPC after chemotherapy with docetaxel. Patients were randomized in a 2:1 ratio to receive oral enzalutamide at a dose of 160 mg per day or placebo. The primary endpoint was OS. The study was stopped after a planned interim analysis at the time of 520 deaths. The median OS was 18.4 months in the enzalutamide group versus 13.6 months in the placebo group (HR 0.63, 95% CI 0.53-0.75, p<0.001). The superiority of enzalutamide over placebo was shown with respect to all secondary endpoints: ≥50% PSA reduction (54% vs. 2%, p<0.001), soft-tissue response rate (29% vs. 4%, p<0.001), the quality-of-life response rate (43% vs. 18%, p<0.001), time to PSA progression (8.3 vs. 3.0 months, p<0.001), time to first SRE (16.7 vs. 13.3 months, p<0.001).

The rates of AEs (Adverse events) between the enzalutamide and placebo group were similar. The enzalutamide group had a lower incidence of AEs of grade 3 or above (45.3% vs. 53.1%). The median time to first AE was 12.6 months in the enzalutamide group compared to 4.2 months in the placebo group. There was a higher incidence of all grades of fatigue, diarrhea, hot flashes, musculoskeletal pain, and headache in the enzalutamide group compared to placebo. Cardiac disorders were noted in 6% of patients receiving enzalutamide and in 8% of patients receiving placebo. Hypertension was observed in 6.6% of patients in the

CONFIDENTIAL

This document is confidential. Do not disclose or use except as authorized.

enzalutamide group compared to 3.3% in the placebo group. LFT abnormalities were reported as AEs in 1% and 2% of the enzalutamide and placebo group, respectively. Five of the 800 patients in the enzalutamide group (0.6%) were reported to have seizures and no seizures were reported in the placebo group. One case of status epilepticus required medical intervention while the other four seizures were self-limited. There were potentially predisposing factors in several patients, including two patients who had brain metastases, one patient who had inadvertently been administered lidocaine intravenously, and one patient with brain atrophy in the context of heavy alcohol use and initiation of haloperidol. Based on the results of this trial, the FDA approved enzalutamide on 8/31/2012 for the treatment of patients with metastatic CRPC who have previously received docetaxel.

The PREVAIL trial is a double-blinded, randomized, placebo-controlled trial is investigating the effectiveness of enzalutamide in patients with metastatic CRPC who have not yet received chemotherapy. The primary endpoints are OS (Overall survival) and PFS (Progression Free Survival). The trial has reached its target accrual of 1,680 patients.

## 2.2 Study Disease

Prostate cancer is the most common cancer in men in the United States, with a life time risk of 16%, and the second leading cause of death in this population. In 2012, it is estimated that 241,740 men will be diagnosed with prostate cancer and 28,170 will die of the disease.

ADT (Androgen Deprivation Therapy) is the mainstay of systemic therapy for patients with prostate cancer. In patients with advanced disease, despite initial response rates of 80-90%, nearly all men develop progressive disease within 18-24 months of therapy. Men with CRPC have a poor prognosis with median survival of 16-18 months and fewer than 20% of patients surviving beyond three years.

## 2.3 Rationale

Recent advances in genomics provide unprecedented opportunities for translational objectives that inform both treatment response and disease biology. Molecular mechanisms of resistance to targeted anti-cancer agents reported in the past few years include secondary mutations in target genes, gene amplification and/or overexpression, generation of alternatively spliced transcripts, production of new fusion genes, mutations in downstream targets and genetic activation of alternate pathways.

The purpose of this study is to elucidate AR related mechanisms of resistance to enzalutamide via assessment of serial CRPC metastasis biopsies. Tumor analysis will include AR sequencing (mutations, splice-variants), AR regulated gene expression, tumor androgen levels, and profiling of enzymes involved in androgen synthesis/metabolism. Additionally, via whole-exome and transcriptome sequencing we

CONFIDENTIAL

This document is confidential. Do not disclose or use except as authorized.

have the opportunity to perform more holistic studies of drug resistance. Additionally, CTCs were measured in Phase I/II trial of enzalutamide and cell numbers were demonstrated to correlate with clinical response. We propose to measure CTCs to assess response to enzalutamide, in addition to analyzing CTCs for mechanisms of androgen resistance.

## 2.4 Correlative Studies Background

The AR gene is located on chromosome Xq11-12 and is a member of the steroid hormone receptor family. The AR is present in benign prostate epithelial cells as well as in all stages and grades of primary and metastatic prostate cancer. The AR is a 110 kDa ligand-activated transcription factor consisting of 917 amino acids that contain three important domains: 1) a carboxy-terminal LBD which binds androgens, 2) a DBD, and 3) a regulatory NTD. Within the NTD lies the AF-1 and AF-5 domains which contain binding sites for transcriptional coregulators and are essential for AR activity. Under normal conditions, inactive AR is found in the cytoplasm of prostate cells and is stabilized by various HSPs, which expose the LBD and allow ligand binding. Once bound to ligand, a conformational change occurs in the AR, causing dissociation of the HSPs, AR dimerization, and AR migration to the nucleus. Once inside the nucleus, the AR DBD binds to specific AREs on the promoter or enhancer regions of androgen-regulated genes. Transcription is enhanced by the binding of coregulators to AF-1.

Recently, it has become clear that resistance to ADT is mediated by upregulation of AR signaling, despite castrate levels of serum testosterone. Proposed mechanisms of resistance to castration include: 1) increased AR expression leading to AR activation in the presence of low levels of ligand, 2) AR gene mutations leading to promiscuous activation of AR signaling by various ligands, 3) AR splice variants leading to constitutive activation of AR signaling, and 4) increased intra-tumor expression of enzymes involved in steroidogenesis.

The AR is expressed at high levels in most cases of CRPC, with the AR gene being amplified in about one third of cases. Mutations in the AR that cause promiscuous activation by ligand have been detected in at least 15-40% of patients after development of resistance. Stranbrough and colleagues profiled the expression signatures of primary and metastatic prostate tumors, including both castration-sensitive and castration-resistant tumors, and found significant increased intratumoral expression of AR and genes converting adrenal androgens to testosterone and DHT in castrate-resistant tumors. Similarly, Montgomery *et al* showed that metastatic prostate cancers from anorchid men express transcripts encoding steroidogenic enzymes and maintain intratumoral androgens at concentrations capable of activating AR target genes and maintaining tumor cell survival.

Altered AR mRNA splicing and synthesis of truncated AR variant proteins lacking the AR LBD is another mechanism that has been postulated to drive overall resistance to

CONFIDENTIAL

This document is confidential. Do not disclose or use except as authorized.

ADT. Although many forms of these splice-variants are maladaptive and lead to a nonfunctioning AR protein, AR variants lacking the LBD but retaining the DBD and NTD are frequently expressed in CRPC metastases and high levels in prostate cancer tissue predict disease progression and shorter survival. AR splice-variant mutants can thereby be rendered insensitive to circulating or local hormone levels. Recently, it was shown the AR gene rearrangements expressing both full-length and AR variants are androgen independent and enzalutamide resistant.

### 3. PARTICIPANT SELECTION

The inclusion and exclusion criteria for enrolling subjects in this study are described in the following sections. If there is a question about the inclusion or exclusion criteria, the investigator should consult with the PI, [REDACTED] and the DFCI study team before enrolling the subject in the study.

#### 3.1 Eligibility Criteria

Participants must meet the following criteria on screening examination to be eligible to participate in the study:

- 3.1.1 Be a male  $\geq 18$  years of age.
- 3.1.2 Participants must have histologically or cytologically confirmed adenocarcinoma of the prostate without  $\geq 50\%$  neuroendocrine differentiation or small cell histology.
- 3.1.3 Participants must have progressive disease as defined by either:
  - Castrate resistant disease as defined by PCWG. Participants must have a rise in PSA on two successive determinations at least one week apart and PSA levels  $\geq 2$  ng/ml (only the screening PSA needs to be  $\geq 2$  ng/ml) and testosterone levels  $< 50$  ng/dL, OR
  - Soft tissue progression defined by RECIST 1.1, OR
  - Bone disease progression defined by PCWG2 with two or more new lesions on bone scan.
- 3.1.4 Participants must have a testosterone levels  $< 50$  ng/dL.
- 3.1.5 CRPC with metastatic disease with at least one site of metastatic disease must be amenable to needle biopsy. Soft tissue biopsy sites include: lymph node or visceral metastases. Bone sites include lumbar vertebrae, pelvic bones and long bones. Excluded sites are thoracic, cervical vertebrae, skull and rib lesions. Biopsy site will be selected with guidance of interventional radiologist determining best site to optimize balance of obtaining useful tissue for analysis and minimizing risk.
- 3.1.6 Participants without orchiectomy must be maintained on LHRH agonist/antagonist therapy.

CONFIDENTIAL

This document is confidential. Do not disclose or use except as authorized.

- 3.1.7 Participants may have had any number of previous hormonal therapies (antiandrogens, estrogens, finasteride, dutasteride, ketoconazole, abiraterone) provided these were discontinued  $\geq 4$  weeks before enrollment. Participants on prednisone 10 mg daily or another equivalent steroid dose are eligible. Participants on inhaled steroids are eligible.
- 3.1.8 Participants may have had up to two previous cytotoxic therapeutic regimens provided these were discontinued  $\geq 4$  weeks before enrollment. The use of antineoplastic agents for non-cancer therapy (i.e. colitis, rheumatoid arthritis) may be allowed provided the patient has been on a stable dose without toxicities greater than grade 1.
- 3.1.9 At least a 4 week interval from previous prostate cancer treatment other than LHRH agonist/antagonist therapy, bisphosphonates, or denosumab to enrollment.
- 3.1.10 Participants receiving bisphosphonates therapy or denosumab can be maintained on this therapy. If participants have not started bisphosphonates or denosumab, it is recommended that they start treatment after the first biopsy.
- 3.1.11 ECOG performance status  $< 2$  (Karnofsky  $>60\%$ , see Appendix A).
- 3.1.12 Participants must have normal organ and marrow function as defined below:
- WBC  $\geq 3,000/\text{mcL}$
  - ANC  $\geq 1,500/\text{mcL}$
  - Platelets  $\geq 100,000/\text{mcL}$
  - Hemoglobin  $\geq 9 \text{ g/dL}$
  - Serum albumin  $\geq 3.0 \text{ g/dL}$
  - AST, ALT, and total bilirubin  $\leq 1.5 \times$  Institutional ULN
  - Creatinine  $\leq 1.5$  Institutional ULN or a calculated creatinine clearance  $\geq 50 \text{ mL/min}$  using the Cockcroft Gault equation
  - PTT  $\leq 60$ , INR  $\leq 1.5$  Institutional ULN unless on warfarin therapy (investigator would need to determine if safe for participant to stop warfarin prior to biopsy)
- 3.1.13 Have signed an informed consent document indicating that the subjects understands the purpose of and procedures required for the study and are willing to participate in the study.
- 3.1.14 Be willing/able to adhere to the prohibitions and restrictions specified in this protocol.
- 3.1.15 Written Authorization for Use and Release of Health and Research Study Information (US sites only) has been obtained.
- 3.1.16 Able to swallow the study drug whole as a tablet.

CONFIDENTIAL

This document is confidential. Do not disclose or use except as authorized.

- 3.1.17 Participants who have partners of childbearing potential must be willing to use a method of birth control with adequate barrier protection as determined to be acceptable by the principal investigator during the treatment period and for 1 week after last dose of enzalutamide.

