#### *Drugs that Inhibit or Induce CYP2C8*

In a drug-drug interaction trial in healthy volunteers, a single 160 mg oral dose of enzalutamide was administered alone or after multiple oral doses of gemfibrozil (strong

CONFIDENTIAL

This document is confidential. Do not disclose or use except as authorized.

CYP2C8 inhibitor). Gemfibrozil increased the composite AUC of enzalutamide plus N-desmethyl enzalutamide by 2.2-fold with minimum effect on  $C_{max}$ . Therefore, co-administration of enzalutamide with strong CYP2C8 inhibitors should be avoided as they would require a dose reduction of enzalutamide, which will not be permitted at study drug initiation. If co-administration of enzalutamide with a strong CYP2C8 inhibitor cannot be avoided, the dose of enzalutamide should be reduced to 80 mg once daily.

The effects of CYP2C8 inducers on the pharmacokinetics of enzalutamide have not been evaluated *in vivo*. Co-administration of enzalutamide with strong or moderate CYP2C8 inducers (i.e. rifampin) may alter the plasma exposure of enzalutamide and should be avoided.

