## 7. DRUG FORMULATION AND ADMINISTRATION

### 7.1 Enzalutamide

Refer to the package insert for enzalutamide information.

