#### 7.1.2 Mechanism of Action

Enzalutamide is an androgen receptor inhibitor that acts on different steps in the androgen receptor signaling pathway. Enzalutamide has been shown to competitively inhibit androgen binding to androgen receptors and inhibit androgen receptor nuclear translocation and interaction with DNA. A major metabolite, N-desmethyl enzalutamide, exhibited similar *in vitro* activity to enzalutamide.

Enzalutamide decreased proliferation and induced cell death of prostate cancer cells *in vitro*, and decreased tumor volume in a mouse prostate cancer xenograft model.

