##### *Absorption*

Following oral administration (enzalutamide 160 mg daily) in patients with metastatic CRPC, the median time to reach Cmax is 1 hour (range 0.5 to 3 hours). At steady state, the plasma mean Cmax values for enzalutamide and N-desmethyl enzalutamide are 16.6 µg/mL (23% CV) and 12.7 µg/mL (30% CV), respectively, and the plasma mean predose trough values are 11.4 µg/mL (26% CV) and 13.0 µg/mL (30% CV), respectively.

With the daily dosing regimen, enzalutamide steady state is achieved by Day 28, and enzalutamide accumulates approximately 8.3-fold relative to a single dose. Daily fluctuations in enzalutamide plasma concentrations are low (mean peak-to-trough ratio of 1.25). At steady state, enzalutamide showed approximately dose proportional pharmacokinetics over the daily dose range of 30 to 360 mg.

A single 160 mg oral dose of enzalutamide was administered to healthy volunteers with a high-fat meal or in the fasted condition. A high-fat meal did not alter the AUC to enzalutamide or N-desmethyl enzalutamide.

CONFIDENTIAL

This document is confidential. Do not disclose or use except as authorized.

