#### *Metabolism*

Following single oral administration of  $^{14}\text{C}$ -enzalutamide 160 mg, plasma samples were analyzed for enzalutamide and its metabolites up to 77 days post dose. Enzalutamide, N-desmethyl enzalutamide, and a major inactive carboxylic acid metabolite accounted for 88% of the  $^{14}\text{C}$ -radioactivity in plasma, representing 30%, 49%, and 10%, respectively, of the total  $^{14}\text{C}$ -AUC0-∞.

*In vitro*, human CYP2C8 and CYP3A4 are responsible for the metabolism of enzalutamide. Based on *in vivo* and *in vitro* data, CYP2C8 is primarily responsible for the formation of the active metabolite (N-desmethyl enzalutamide).

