#### *Elimination*

Enzalutamide is primarily eliminated by hepatic metabolism. Following single oral administration of  $^{14}\text{C}$ -enzalutamide 160 mg, 85% of the radioactivity is recovered by 77 days post dose: 71% is recovered in urine (including only trace amounts of enzalutamide and N-desmethyl enzalutamide), and 14% is recovered in feces (0.4% of dose as unchanged enzalutamide and 1% as N-desmethyl enzalutamide).

The mean apparent clearance of enzalutamide in patients after a single oral dose is 0.56 L/h (range 0.33 to 1.02 L/h).

The mean terminal  $t_{1/2}$  for enzalutamide in patients after a single oral dose is 5.8 days (range 2.8 to 10.2 days). Following a single 160 mg oral dose of enzalutamide in healthy volunteers, the mean terminal  $t_{1/2}$  for N-desmethyl enzalutamide is approximately 7.8 to 8.6 days.

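### Criterion 3.1.17 ends required contraception 1 week after the last dose, about one half-life of the drug and its active metabolite, when roughly half to two-thirds of the combined plasma level remains at mean half-lives

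*Combined protocol and SAP*

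**What the plan says.** Section 3.1, criterion 3.1.17, asks for adequate barrier contraception "during the treatment period and for 1 week after last dose of enzalutamide". It gives no reason for the length of that interval, and no other section of the protocol sets a longer one.

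Section 7.1.3 (Elimination) reports that the mean terminal half-life of enzalutamide "in patients after a single oral dose is 5.8 days (range 2.8 to 10.2 days"), and that the corresponding figure "for N-desmethyl enzalutamide is approximately 7.8 to 8.6 days", the latter from healthy volunteers. Section 7.1.3 (Absorption) states that at steady state "the plasma mean predose trough values are 11.4" µg/mL for the parent, with 13.0 µg/mL for the metabolite.

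The metabolite is pharmacologically relevant on the protocol's own account. Section 7.1.2 says "A major metabolite, N-desmethyl enzalutamide, exhibited similar" in vitro activity to the parent, and section 7.1.3 (Metabolism) says "CYP2C8 is primarily responsible for the formation of the active metabolite (N-desmethyl enzalutamide"). Section 5.3 also adds the two together when it describes an interaction, using the "composite AUC of enzalutamide plus N-desmethyl enzalutamide".

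For drug information generally, section 7.1 says "Refer to the package insert for enzalutamide information".

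**The concern.** The protocol has already judged contraception necessary while these men take the drug, although they are castrate (3.1.4, 3.1.6). A post-treatment interval normally exists to let the drug clear. One week is 7/5.8 = 1.2 mean half-lives of the parent and 7/8.6 to 7/7.8 = 0.8 to 0.9 half-lives of the metabolite, so little of that clearance has happened when the requirement lapses.

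What is at stake is possible exposure of a partner or a pregnancy in the weeks after the last dose. No efficacy or correlative result depends on it.

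**Working it through.** **Inputs.** Interval 7 days (3.1.17). Parent half-life hp = 5.8 days, range 2.8 to 10.2, and metabolite half-life hm = 7.8 to 8.6 days (7.1.3, Elimination). Steady-state troughs 11.4 and 13.0 µg/mL, sum 24.4; steady-state Cmax 16.6 and 12.7 µg/mL, sum 29.3 (7.1.3, Absorption). Volume 110 L and clearance 0.56 L/h (7.1.3).

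**Check of the protocol's half-life.** ln 2 × 110 / 0.56 = 136.2 h = 5.67 days, against 5.8 stated (2.2% lower). At 5.8 days, 1 − 2^(−28/5.8) = 96.5% of steady state is reached by day 28, which agrees with the protocol's statement that steady state is achieved by then.

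**Formulas.** With kp = ln 2/hp and km = ln 2/hm, as fractions of the steady-state level:

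- Parent: p(t) = 2^(−t/hp).
- Metabolite, simple decline: m(t) = 2^(−t/hm).
- Metabolite with formation from remaining parent: f(t) = (km·e^(−kp·t) − kp·e^(−km·t)) / (km − kp).
- Combined from trough: (11.4·p + 13.0·m) / 24.4, or the same with f in place of m. From Cmax: weights 16.6 and 12.7 over 29.3.

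For given half-lives, simple decline understates what remains, because the parent still present keeps forming metabolite.

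**Day 7 at the mean parent half-life.** p = 2^(−7/5.8) = 0.433; m = 0.537 to 0.569; f = 0.837 to 0.850.

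- Simple, from trough: 11.92/24.4 = 48.8% to 12.33/24.4 = 50.5%.
- With formation, from trough: 15.82/24.4 = 64.9% to 15.99/24.4 = 65.5%.

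**Day 7 across the stated parent range** (each span covers hm = 7.8 to 8.6):

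| Start | hp (days) | Simple decline | With formation |
|---|---|---|---|
| Trough | 2.8 | 36.9-38.6% | 47.6-48.6% |
| Trough | 5.8 | 48.8-50.5% | 64.9-65.5% |
| Trough | 10.2 | 57.6-59.3% | 76.8-77.2% |
| Cmax | 2.8 | 33.3-34.7% | 42.0-42.9% |
| Cmax | 5.8 | 47.8-49.2% | 60.8-61.4% |
| Cmax | 10.2 | 58.5-59.9% | 74.1-74.4% |

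Section 2.1.1 separately reports a half-life of about 1 week from the phase I/II study. Using 7 days for the parent gives 52-54% (simple) or 69-70% (with formation) from trough.

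**Scale against the protocol's own doses.** Section 7.1.3 describes approximately dose-proportional steady-state kinetics from 30 to 360 mg. On that basis the day-7 parent level corresponds to 0.433 × 160 = 69 mg daily. The combined level by simple decline corresponds to 0.488 × 160 = 78 mg to 0.505 × 160 = 81 mg; with formation it is higher (0.649 × 160 = 104 mg). Dose level −2 in section 6 is 80 mg daily, and a participant on it is still in the treatment period, so 3.1.17 still applies to him.

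**A longer interval.** Five half-lives at 8.6 days = 43 days. With formation, from trough, the combined level then is:

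- hp = 5.8: p = 0.006, f = 0.068 to 0.084, combined 3.9-4.7%.
- hp = 10.2: p = 0.054, f = 0.158 to 0.175, combined 10.9-11.9%.

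**The case against.** The strongest objection is that the documents supply no standard that 1 week fails. They contain no reproductive-toxicity data, no semen-transfer data and no exposure threshold. Plasma level in a man does not measure exposure of a partner or fetus. The instruction in section 7.1.5 about pregnant women concerns handling the capsules only. This stands: a reader might infer that 1 week exposes partners to harm, and the documents do not support that. They show that active drug remains.

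A second objection is that section 7.1 defers to the package insert, and neither the insert nor the consent form was available for review. A reader might infer that the protocol contradicts the label, or that participants receive no longer advice. Neither can be concluded.

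Third, it is tempting to say that at least half remains in every participant. That fails for fast eliminators: at a 2.8-day half-life the figure is 37-39% by simple decline from trough, and 42-43% from Cmax even with formation.

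Finally, participants have castrate testosterone, and 3.1.17 sets a minimum that investigators may exceed. Both points limit the importance of the matter. Neither explains why a precaution required in the same castrate men at 80 mg daily may stop at a similar plasma level.

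**Conclusion.** The concern holds as a minor partner-safety point. The required period covers about one half-life of parent and active metabolite, and at mean half-lives roughly half to two-thirds of the combined steady-state level is still present when it ends: 49-51% from trough by simple decline, about 61-65% with formation. With formation, the span over the stated parent half-lives and either starting level is about 42-77%.

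These figures rest on several assumptions:

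- One-compartment, linear decline, although section 7.1.3 describes a two-compartment parent model.
- The single-dose, healthy-volunteer metabolite half-life applies to patients at steady state.
- Mean steady-state levels apply across the half-life range.
- Parent and metabolite are added 1:1.

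The comparison with the 80 mg dose level also assumes that dose-proportionality extends to the metabolite. Five half-lives is a convention, not a rule in the protocol.

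That few participants are likely to be affected is a judgement; the documents give no count of those with partners of childbearing potential. Sample size, visits and analyses are unaffected. It is worth raising as a cheap improvement.

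**What to change.** In 3.1.17, replace 1 week with a washout-based interval of about 6 weeks (43 days), or with the package-insert interval if that is longer. Use the same interval in the participant instructions, and state its basis in one sentence.

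Six weeks leaves about 4-5% of the combined level at the mean parent half-life and about 11-12% at the slowest stated one, so it does not give complete washout for every participant.

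The cost is an edit to one criterion and the matching instructions, plus 43 − 7 = 36 days, about 5 more weeks, of contraception for participants with partners of childbearing potential.
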